3.1 Study Population

The domain study population covers participant disposition, analysis sets, IPDs, demographics, baseline characteristics, medical history, and prior and concomitant medication.

3.1.1 Participant Disposition and Completion Status

3.1.1.1 Definitions and Derivations

Participants that signed the Informed Consent Form (ICF) will be considered as enrolled participants. For screen failure participants, the reason for screen failure will be reported.

Participants that met all the eligibility criteria will be considered as assigned to the study intervention. Participants with at least one treatment start date will be considered as participants that started the study intervention.

Participants that have the standardized disposition term "Completed" will be considered as having completed the study. Participants that have the standardized disposition term "Screen Failure" will be considered as screening failures. All other participants will be considered as assigned to the study intervention and withdrawn from the study, with the reason reported as the standardized disposition term.

Participants that did not permanently discontinue the study according to the Discontinuation of Study Intervention form will be considered as having completed the treatment. The main reason for study intervention discontinuation will be summarized.

3.1.1.2 Presentation

Participant disposition and completion status will be summarized for all enrolled participants and reported as the number and percentages of:

- screened participants
- screen failures and the reason for screen failure
- participants assigned to the treatment
- participants assigned to treatment but not treated
- participants that started the study intervention, and among these the number and percentage of:
 - participants that completed or discontinued the study intervention
 - participants that completed the study or were withdrawn from the study

3.1.2 Analysis Sets

3.1.2.1 Definitions and Derivations

The populations to be analyzed are defined in Section 2.2 and comprise:

- Participants who completed the study per protocol definition and had no acute asthma exacerbation nor lower respiratory tract infection during the study period (primary analysis population)
- All participants who completed the study per protocol definition (evaluable population)
- Participants who completed baseline measurements at Visit 1 and had at least one dose of study intervention, irrespectively of whether they completed the study or were discontinued for reasons as described in Section 7.1 of the CSP (the baseline endpoints analysis set)

Sub-populations to be analyzed include:

- Mucus plugging status: Participants with (mucus plug score different from 0) or without mucus plugs (mucus plug score equal to 0) identified using CT scans (see Section 8.1.1.2 of the CSP) taken at Visit 1 (Week 0)
- Oral corticosterioids (OCS) dependency status: OCS-dependent and Non-OCS-dependent participants as defined by inclusion criteria 4 (see Section 5.1 of the CSP)

Safety analyses will be performed on the safety analysis set.

3.1.2.2 Presentation

The number of participants included in each analysis set will be reported, as well as the number of excluded participants from each analysis set.

3.1.3 Protocol Deviations

3.1.3.1 Definitions and Derivations

Definitions of IPDs are available in Section 2.3.5.

3.1.3.2 Presentation

The number and percentage of participants with any IPD in the primary analysis set and in the evaluable analysis set will be reported. The number and percentage of participants with any IPD will also be reported according to the category of IPDs listed in Section 2.3.5.

3.1.4 Demographics

3.1.4.1 Definitions and Derivations

Demographic characteristics to be assessed include age (years), sex, race, ethnic group, and country. Age groups 18 to 64 and 65 to 75 will also be presented (for EudraCT reporting).

3.1.4.2 Presentation

Demographics will be summarized for the primary analysis set and the evaluable set. Age will be summarized using mean, SD, median, minimum, and maximum. Age groups, race, ethnic group, and country will be summarized using number and percentage of participants.

3.1.5 Baseline Characteristics

3.1.5.1 Definitions and Derivations

Height (cm), weight (kg), Body mass index (BMI) calculated as: BMI (kg/m²) = weight(kg)/height(cm)²), and electrocardiogram (ECG) results at screening will be summarized.

3.1.5.2 Presentation

Baseline characteristics will be summarized for the primary analysis set and evaluable. Continuous variables, i.e., height, weight, and BMI, will be summarized using mean, SD, median, minimum, and maximum. Categorical variables, i.e., ECG results and will be summarized using number and percentage of participants.

3.1.6 Disease Characteristics

3.1.6.1 Definitions and Derivations

Asthma history details will be reported, including:

- time since asthma diagnosis
- time since last exacerbation
- number of exacerbations in the previous 12 months and asthma exacerbation details (systemic corticosteroids, increase in a stable oral corticosteroid background dose, associated Emergency Room (ER) visits or hospitalization).
- Global initiative for asthma (GINA) classification
- previously required mechanical ventilation

Time since asthma diagnosis is calculated as follows:

((Screening date – Asthma diagnosis date) + 1)/365.25.

Time since last exacerbation is calculated as follows:

(Screening date - Last exacerbation date) + 1.

If the day of diagnosis is missing then this will be imputed as the 1st of the month. Missing month will be imputed as June, unless diagnosis year is the same as the year of informed consent and the informed consent date is on or before June. Then, we will impute month as the latest month in which the 1st is before the informed consent date.

Completely missing dates will not be imputed; time since diagnosis will be set to missing and reported as n (%) missing. Time since diagnosis will be summarised across patients with a complete or partial data recorded.

Asthma exacerbation is defined by a worsening of asthma requiring:

- Use of systemic corticosteroids (or a temporary increase in a stable oral corticosteroid background dose) for at least 3 days; a single depo-injectable dose of corticosteroids will be considered equivalent to a 3-day course of systemic corticosteroids
- An ER/urgent care visit (defined as evaluation and treatment for < 24 hours in ER or urgent care center) due to asthma that required systemic corticosteroids (as per above)

• An inpatient hospitalization due to asthma (defined as an admission to an inpatient facility and/or evaluation and treatment in a healthcare facility for ≥ 24 hours)

3.1.6.2 Presentation

Time since asthma diagnosis (days), time since last exacerbation (days), number of exacerbations will be summarized using mean, SD, median, minimum, and maximum. Asthma exacerbation details (systemic corticosteroids, increase in a stable oral corticosteroid background dose, associated ER visits, or hospitalization), GINA classification, and previously required mechanical ventilation will be summarized using number and percentage per category. Summaries will be presented for the primary analysis and evaluable sets.

By-participant listings will be provided for the enrolled participant.

3.1.7 Medical History and Concomitant Disease

3.1.7.1 Definitions and Derivations

Medical and surgical history will be coded according to the most recent MedDRA version and summarized by System Organ Class (SOC) and preferred term.

3.1.7.2 Presentation

Medical and surgical history and concomitant illness will be listed by participant in the enrolled population including description of the disease/procedure, start date and stop date (or ongoing if applicable) based on the safety analysis set.

The number and percentage of participants with any relevant medical history, surgical history, and concomitant illness will be reported overall in the primary analysis set and in the evaluable analysis set, by SOC and preferred term.

Respiratory medical history will be reported in a separate table and listing.

3.1.8 **Prior and Concomitant Medications**

3.1.8.1 Definitions and Derivations

Prior medication stopped before signing the ICF, as well as all concomitant medications taken during the conduct of the study, will be described.

Prior and concomitant medication will be coded according to the World Health Organization Drug Dictionary (WHODrug), version March 2020 or later.

Medication start and stop dates will be compared to the date of first dose of study medication to allow medications to be classified as either prior only, both prior and concomitant, or concomitant only. Medications starting after the completion/withdrawal date will be listed but will not be classified or summarized. Medications that started and stopped prior to the time of enrolment (Visit 1) will be considered as prior medications. Any medication or vaccine (including over-the-counter or prescription medicines, vitamins, and/or herbal supplements, or other specific categories of interest) that the participant is receiving at the time of enrolment or during the study will be recorded as concomitant.

If a medication starts before signing the ICF and stops after signing the ICF then the medication will be classified as both prior and concomitant. Medications will be classified as concomitant only if they have a start date on or after signing the ICF and during the study conduct (ie, during the study follow-up period).

If medication start and/or stop dates are missing or partial, the dates will be compared as far as possible with the date of signing the ICF. Medications will be assumed to be concomitant only, unless there is clear evidence (through comparison of partial dates) to suggest that the medication started prior to signing the ICF. If there is clear evidence to suggest that the medication started prior to signing the ICF, the medication will be assumed to be both prior and concomitant, unless there is clear evidence to suggest that the medication stopped prior to signing the ICF. If there is clear evidence to suggest that the medication stopped prior to signing the ICF. If there is clear evidence to suggest that the medication stopped prior to signing the ICF. If there is clear evidence to suggest that the medication stopped prior to signing the ICF, the medication will be assumed to be prior only.

3.1.8.2 Presentation

Prior and concomitant medications will be listed by participant in the enrolled population, and will include the following information: reported name, Anatomical Therapeutical Chemical Classification (ATC), and generic drug name, the route of administration, dose, frequency, start date/time, and duration and indication.

A summary of prior and concomitant medications received, by ATC level 4 code and generic drug name overall will be reported on the primary analysis set, evaluable analysis set, and safety analysis set. Prior medications that continue after the date of first dose will also be reported and classified in both prior and concomitant medication groups.

The duration of medication will be calculated as:

- Duration (in hours) = (end date/time start date/time)/3600; in case date and time is available.
- Duration (in days) = (end date start date) + 1, in case only the date is provided.

The duration will be reported in days in the listing. For medications with partial or completely missing start date/times and/or end date/times, the duration will not be calculated.

Multiple records for a participant in the same ATC level 4 category and generic drug name will be counted only once.

3.1.9 Study Drug Compliance

3.1.9.1 Definitions and Derivations

Not applicable.

3.1.9.2 Presentation

Not applicable.

3.1.10 Sample Size Analysis

3.2 Endpoint Analyses

This section covers details related to the primary, secondary, tertiary, and safety endpoints, including sensitivity and supportive analyses. A summary of the planned endpoint analyses is provided in Table 3.

Details

category	Endpoint	Population	strategy	summary (analysis)	in Section
Primary objec benralizumab	ctive – To describe the c , using measurements f	hange from baselin rom untrimmed air	e in mucus volume at rways at TLC and irre	week 13 following treat spective of patient chara	ment with acteristics
Primary	Change from baseline (Week 0) at week 13 (± 5 days) in untrimmed total mucus volume at TLC	Evaluable set; Primary analysis population	Included in analysis regardless of treatment discontinuation, any IPD or any prohibited medication (treatment policy); Participants with exacerbations are excluded from the primary analysis set	Unadjusted mean within participant difference in untrimmed total mucus volume calculated as the mean change from baseline (Week 0) at Week 13 (± 5 days).	3.2.1
Secondary obj treatment with	jective 1 – To describe t h benralizumab, as mea	he change from ba sured by secondar	seline in airway dynan y FRI endpoints, irresj	nics at Week 13 followin pective of patient charac	g cteristics.
Secondary	Change from baseline (Week 0) at week 13 in primary and secondary FRI parameters ^a	Evaluable set; Primary analysis population	Included in analysis regardless of treatment discontinuation, any IPD or any prohibited medication (treatment policy); Participants with exacerbations are excluded from the primary analysis set	Unadjusted mean within participant difference, calculated as the mean change from baseline (Week 0) at Week 13 (± 5 days), in listed FRI endpoints.	3.2.2
Secondary obj measurements	jective 2 – To describe t s, cross-sectionally (at V	the relationship bet Veek 0) and irrespe	ween airway dynamics ective of patient charac	s and conventional lung cteristics.	function
Secondary	Baseline (Week 0) relationship between pre-BD FEV1 and: In primary and secondary FRI parameters ^a	Evaluable set; Primary analysis population; Baseline endpoints analysis set	Included in analysis regardless of treatment discontinuation, any IPD or any prohibited medication (treatment policy). Participants with exacerbations are excluded from the	 Spearman's rank correlation coefficient Pearson correlation Graphical summary (scatterplots) Regression coefficients with 95% CI 	3.2.3

excluded from the primary analysis set

Summary of Endpoint Analyses Table 3

STATISTICAL ANALYSIS PLAN D3250R00107 - ed. 2.0

Statistical category	Endpoint	Population	Intercurrent event strategy	Population level summary (analysis)	Details in Section
Secondary	Baseline (Week 0) relationship between pre-BD FVC and: FRI parameters ^a	Baseline endpoints analysis set	Included in analysis regardless of treatment discontinuation, any IPD or any prohibited medication (treatment policy). Participants with exacerbations are excluded from the primary analysis set	 Spearman's rank correlation coefficient Pearson correlation Graphical summary (scatterplots) Regression coefficients with 95% CI 	3.2.3
Secondary objective 3 – 10 describe the relationship between changes from baseline (Week 0) in airway dynamics and conventional lung function measurements at Week 13, after accounting for baseline measurements of conventional lung function.			ıy		
Secondary	Relationship between change from baseline (Week 0 to 13) in pre-BD FEV1 and: FRI parameters ^a	Primary analysis population	Included in analysis regardless of treatment discontinuation, any IPD or any prohibited medication (treatment policy). Participants with exacerbations are excluded from the primary analysis set	 Spearman's rank correlation coefficient Pearson correlation Graphical summary (scatterplots) Regression coefficients with 95% CI 	3.2.4
Secondary	Relationship between change from baseline (Week 0 to 13) in pre-BD FVC and: FRI parameters ^a	Primary analysis population	Included in analysis regardless of treatment discontinuation, any IPD or any prohibited medication (treatment policy). Participants with exacerbations are excluded from the primary analysis set	 Spearman's rank correlation coefficient Pearson correlation Graphical summary (scatterplots) Regression coefficients with 95% CI 	3.2.4

D3250R00107 - ed. 2.0

AstraZeneca 16-Feb-2024

Statistical category Safety – To m	Endpoint onitor the safety and to	Population lerability of benral	Intercurrent event strategy izumab.	Population level summary (analysis)	Details in Section
Safety	Safety and tolerability will be evaluated in terms of AEs, vital signs, and clinical laboratory.	Safety analysis set	Included in analysis regardless of treatment discontinuation, any IPD or any prohibited medication (treatment policy).	Descriptive statistics: number of participants and percentage for categorical variables, mean, SD, median, minimum, maximum, for measured values at each timepoint and changes from baseline	3.6.2, 3.6.3, 3.6.6

D3250R00107 - ed. 2.0

AstraZeneca 16-Feb-2024

	Statistical category	Endpoint	Population	Intercurrent event strategy	Population level summary (analysis)	Details in Section	
CC	1						
	CCI						

D3250R00107 - ed. 2.0

-

AstraZeneca 16-Feb-2024

_	Statistical category	Endpoint	Population	Intercurrent event strategy	Population level summary (analysis)	Details in Section

D3250R00107 - ed. 2.0

	Statistical category	Endpoint	Population	Intercurrent event strategy	Population level summary (analysis)	Details in Section
CCI						

The primary FRI parameter is untrimmed total mucus volume at TLC; secondary FRI parameters include: air trapping at FRC; iVaww at TLC; siVaw at TLC and FRC; iVlung at TLC and FRC; and mucus plugs score (Table 2).

3.2.1 Primary Endpoint – Change from Baseline (Week 0) to week 13 in airway dynamics, using untrimmed total mucus volume at TLC

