2 DATA ANALYSIS CONSIDERATIONS

2.1 Timing of Analyses

The analyses will be performed after the end of study. No interim analyses are planned.

2.2 **Analysis Populations**

The analysis data sets are defined as reported in Table 1.

Population/Analysis Set	Description
Enrolled	All participants who sign the informed consent form
Evaluable	All participants who have completed three doses of study intervention and have baseline and post-benralizumab treatment study evaluation (PROs, CT scans, and spirometry tests) – the evaluable population.
Baseline endpoints analysis set	Participants who have baseline measurements and who have had at least one dose of study intervention. Irrespectively of whether they were discontinued for reasons described in Section 7.1 of the CSP will be included for analyses conducted on the study population who at least started study intervention.
Primary analysis population	The portion of the evaluable population that did not have any acute asthma exacerbation nor lower respiratory tract infection during the study period will be the primary analysis population for the endpoints in this study.
Safety analysis set	The safety analysis set consists of all participants who have received at least one dose of study intervention.

Analysis Data Sets Table 1

PRO Patient Reported Outcomes

2.3 **General Considerations**

In this study, Functional Respiratory Imaging (FRI) will be used to measure changes in airway dynamics. The FRI endpoints are defined in Table 2.

Table 2	Functional Respiratory Imaging Parameters				
Parameter from	Description	Parameter	Anticipated Data Selection		
Ductocol	_	from data	_		

Parameter from Protocol	Description	Parameter from data transfer	Anticipated Data Selection Specifications
Untrimmed total mucus volume at TLC (Primary)	Mucus volume	CCI	
Untrimmed total mucus plugs score at TLC (secondary)	Mucus plugs score		
Total air trapping at FRC (secondary)	Air trapping		
Trimmed distal specific iVaww at TLC(secondary)	Airway wall volume		

Parameter from Protocol	Description	Parameter from data transfer	Anticipated Data Selection Specifications
Trimmed distal specific siVaw at TLC (secondary)	Specific airway volume	CCI	
Trimmed distal specific siVaw at FRC (secondary)	Specific airway volume		
Total iVlung at TLC (secondary)	Lung volume		
Total iVlung at FRC (secondary)	Lung volume		
Ċ			

, FRC Functional residual capacity, TLC Total lung capacity

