3.2.1.3 Handling of Dropouts and Missing Data

The analysis populations will only include participants who have completed 3 doses of study intervention and have baseline and post-benralizumab treatment study evaluation (PROs, CT scans, and spirometry tests). To that end, participants withdrawing before Week 13 and participants with missing mucus volume measurements at Week 0 or Week 13 will not be included in the analysis.

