3.2.1.6 Sensitivity Analyses of the Primary Endpoint

Not applicable.

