1.1 Analysis Population

There is a required update to the SAP which will differ from the CSP. It related to the analysis populations in section 2.2 of the SAP. The analysis populations are taken directly form the CSP but has led to a misinterpretation which in turn has led to data being missed from the analysis which could be utilized.

The update relates to the Evaluable analysis set but impacts the Primary analysis set as well. The updated definition is outlined in Table 1.

Population/Analysis Set	Description
Evaluable	All participants who have completed three doses of study
	intervention and have baseline and post-benralizumab treatment
	study evaluation in at least one of PROs, CT scans, or spirometry
	tests – the evaluable population.

Table 1 Analysis Data Sets

The update resolves the issue that a missing PRO, for example, would lead to available spirometry tests or CT scan data not being presented. It has been clarified that only one of these need to be present to be included in the analysis set.

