2.14 Incomplete Scans

During the dry run it was noted that some participants had baseline definitions of a subset of the FRI parameters. This incompleteness led to them being excluded from further assessment. The

Parexel International

Developed from TP-BPM-WW-032; related to SOP-BPM-WW-001 D3250R00107

Statistical Analysis Plan Addendum

expectation was that if a scan was performed that all FRI parameters would be measured. This inconsistency has resulted in the following update.

Those participants who have incomplete FRI parameters and are missing their baseline or Week 13 assessment will be excluded from the analysis of those parameters. They will, however, remain in the analysis population.

Signature Page for VV-RIM-06725225 System v3.0 d3250r00107 SAP Addendum v3.0

Signature Page for VV-RIM-06725225 System v3.0 d3250r00107 SAP Addendum v3.0

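### SAP Table 3 claims a treatment-policy strategy for discontinuation in the primary, secondary 1 and secondary 3 rows, but those analyses can include only participants with three doses and paired measurements

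*SAP*

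**What the plan says.** SAP section 3.2, Table 3, gives the primary row the strategy "Included in analysis regardless of treatment discontinuation, any IPD or any prohibited medication (treatment policy" and adds that participants with exacerbations are left out of the primary analysis set. The rows for secondary objectives 1 and 3 carry the same text. The populations named are the Evaluable set and the Primary analysis population for the primary and secondary 1 rows, and the Primary analysis population alone for secondary 3.

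SAP section 2.2, Table 1, defines the Evaluable set as "All participants who have completed three doses of study intervention and have baseline and post-benralizumab treatment study evaluation (PROs, CT scans, and spirometry tests". The Primary analysis population is "The portion of the evaluable population that did not have any acute asthma exacerbation nor lower respiratory tract infection during the study period". Section 3.2.1.3 repeats the dosing condition for the primary endpoint: "The analysis populations will only include participants who have completed 3 doses of study intervention". It continues: "participants withdrawing before Week 13 and participants with missing mucus volume measurements at Week 0 or Week 13 will not be included". Sections 3.2.2.3 and 3.2.4.3 apply matching rules to secondary endpoints 1 and 3.

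Addendum v3.0, section 1.1, relaxes the assessment condition to "study evaluation in at least one of PROs, CT scans, or spirometry" tests but keeps the three doses. Addendum section 2.14 keeps participants with incomplete imaging in the population, but those "missing their baseline or Week 13 assessment will be excluded from the analysis of those parameters".

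SAP section 3.2.1.6, "Sensitivity Analyses of the Primary Endpoint", is marked not applicable. So is section 3.2.1.7 on supplementary analyses.

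**The concern.** A treatment-policy strategy uses the outcome at the planned time whether or not treatment was stopped. That requires the outcome to be measured after stopping and participants who stopped to be in the analysis set. Here the set is defined by completing treatment. With only three doses planned, anyone who stops during the dosing course is excluded by definition.

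What is at stake is what the trial may claim. A reader who relies on the strategy column would take the mean change as holding for everyone who started benralizumab. It holds for those who finished dosing and were scanned twice. Some stopping criteria in protocol section 7.1 concern the disease itself, such as asthma events leading to hospitalization or intubation, so the exclusions may be related to outcome. A single-arm trial has no comparator in which such selection would show.

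**Working it through.** **Step 1: who can enter the mucus-volume analysis?**
- Stops before dose three: outside both sets (SAP section 2.2; Addendum section 1.1).
- Stops or leaves after dose three but before Week 13: excluded by SAP section 3.2.1.3. Protocol section 7.1 sends such participants to the early-discontinuation procedures.
- Completes three doses but lacks a baseline or Week 13 mucus volume: under the Addendum stays in the Evaluable set, but is dropped from this parameter (Addendum section 2.14).
- Completes three doses with both values but has an exacerbation or lower respiratory tract infection: outside the Primary analysis population, inside the Evaluable analysis.

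The discontinuation clause in Table 3 therefore has almost nobody to act on.

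**Step 2: could a treatment-policy estimate be produced?** The protocol's Schedule of Activities marks CT at Visits 1 and 4 only, with none at the early-discontinuation visit. Section 8.1.1.1 agrees. The synopsis counts stopping benralizumab as study withdrawal, whereas section 7.1 keeps such participants in the study for safety evaluation. These two passages must be reconciled, but neither provides a later scan.

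**Step 3: which parts of the label hold?** Neither set excludes participants for protocol deviations or prohibited medication, so that wording is consistent. The safety row uses the Safety analysis set. SAP section 3.2.3 places secondary 2 on the Baseline endpoints analysis set. Both of these need only one dose, so the label fits there.

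**Step 4: illustrative size.** The protocol synopsis plans 38 enrolled, 34 evaluable and 29 in the primary analysis. The 29 cannot be reproduced because the assumptions in section 9.2 are blacked out; nothing here depends on it. Under the protocol's definition each of the 34 has both scans.

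Let f be the share analyzed, and r the mean change in the excluded divided by that in the analyzed. Then

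mean over all / mean over analyzed = f + (1 − f) × r.

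With f = 34/38 = 0.895 and 1 − f = 4/38 = 0.105:
- r = 1: 1.00
- r = 0.5: 0.895 + 0.105 × 0.5 = 0.95
- r = 0: 0.89 (34/38 = 0.8947)
- r = −1: 0.895 − 0.105 = 0.79

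The values of r are assumptions. The 38 is also uncertain as a denominator, because SAP Table 1 counts as enrolled everyone who signs consent. On the planned counts the number dosed lies between 34 and 38, so the loss among dosed participants lies between 0/34 = 0% and 4/38 = 10.5%. The zero-change factor then lies between 1.00 and 0.89.

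**The case against.** The strongest reply is that the documents already disclose the restriction. The Table 3 rows name their populations, section 3.2.1.3 states the exclusions plainly, and sections 3.1.1.2 and 3.1.2.2 require counts of discontinuations, withdrawals and participants left out of each set. This is also a small mechanistic study with a descriptive objective, analyzed in two sets. Most of this stands: a careful report would not hide the restriction. It does not rescue the label, which contradicts those same sections, and neither analysis set includes participants who stopped early.

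Four stronger readings are tempting and not supported.

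- A reader might infer that the whole gap from 38 to 29 measures this defect. Of that gap, 34 − 29 = 5 are planned Evaluable participants with an exacerbation or infection. Their measured change is analyzed in the Evaluable set, and Table 3 openly declares the exacerbation exclusion.
- A reader might infer that the sets themselves require a Week 13 scan. Under the Addendum they do not; the requirement now acts parameter by parameter.
- A reader might infer that the estimate is biased toward benefit. Section 7.1 also lists participant decision, pregnancy, non-compliance and COVID-19, and no outcome data on those who stop are given. Informative exclusion is plausible, not shown.
- A reader might infer that SAP Tables 4, 5 and 7 need the same correction. They list intercurrent events without a treatment-policy label.

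**Conclusion.** The concern holds for the discontinuation clause in the primary, secondary 1 and secondary 3 rows of Table 3. The stated strategy is not the one applied, the design does not collect the scans it would need, and the Addendum leaves the mismatch in place. For the primary endpoint, the result describes participants who received three doses and have both mucus-volume measurements.

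The contradiction rests on the text alone. Its numerical consequence is unknown: the 0.89 factor assumes that 4 of 38 dosed participants are lost with exactly zero change, and the planned number dosed is not visible. This should be corrected because it governs what population the result may be said to represent. It does not invalidate the paired analysis in the participants it includes.

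**What to change.** In the three affected sets of rows in Table 3, replace the discontinuation clause with wording such as *participants who completed three doses and have paired Week 0 and Week 13 measurements*. Leave the protocol-deviation and prohibited-medication wording, the safety row and the secondary 2 analysis on the Baseline endpoints set as they are. Report the number of dosed participants excluded from the mucus-volume analysis, with reasons.

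Add one sensitivity analysis of the primary endpoint in all dosed participants with a baseline CT. Use the observed Week 13 value wherever one exists, including for completers with exacerbations. Where none exists, apply a delta or tipping-point range that includes zero change, preferably through multiple imputation. A single fixed zero would understate uncertainty and would not be conservative if those who left had worsened. Specify the range before the final analysis; if that is no longer possible, label the analysis post hoc. It will not be a treatment-policy estimate, but it will show how far the result depends on the missing participants.

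The cost is a wording change, one extra table and possibly a less favorable estimate. No new visits or scans are needed.
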